Abstract: Polycystic ovarian syndrome (PCOS) is one of the common endocrine diseases that lead to female reproductive dysfunction. Up to 75% of PCOS patients have endocrine and metabolic abnormalities such as obesity, hyperinsulinemia and hyperandrogenemia. As a classic PCOS drug, CPA/EE is mainly used to adjust estrogen and progesterone levels and menstrual cycle. Recent studies have found that this drug may worsen blood lipids and reduce insulin sensitivity. On the other hand, studies have found that reproductive disorders secondary to metabolic disorders can be improved by correcting metabolic disorders. glucagon-like peptide1 receptor agonist (GLP-1 RA) is a new type of glucagon-like peptide1 receptor agonist, which has a significant effect on the improvement of metabolic disorders in obese patients. This topic aims to study. To observe the effects of metformin combined with CPA/EE or GLP-1RA on blood glucose, blood lipids, sex hormone levels and menstrual cycle in overweight PCOS patients.

Sponsor/Contact Person/Phone Number	Xinqiao Hospital Endocrinology Department/ [name] /[name]
Research department/project leader	Endocrinology Department / [name]
Research category	Clinical research, source: self raised
Title of the study	The Effect of GLP-1 Agonists Versus OCs on Reproductive Disorders and Cardiovascular Risks in Overweight PCOS
NTC Number	NCT03151005
Research duration	3 years
Number of research and design cases in this center	60 cases

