Study design	All subjects underwent height, weight, waist and hip, hip circumference, blood pressure, hairy score, blood biochemistry (blood routine, liver and kidney function, electrolyte, thyroid function, fasting blood glucose, glycated hemoglobin, insulin release test, inflammatory markers, sex hormones, eight items), gynecologic color Doppler ultrasound and glucose clamp examination before admission. After informed consent was obtained, 1ml of the remaining plasma was collected and frozen in the refrigerator at -80°C. Patients with $BMI \geq 24 \text{ kg/m}^2$ or waist circumference $\geq 85 \text{ cm}$ were randomly assigned to GLP-1RA + metformin or Diane-35 + metformin. After 1 month, all subjects were examined: height, weight, BMI, waist circumference, hip circumference, waist-to-hip ratio, menstrual history, hirsutism score, diet, exercise frequency and intensity, blood pressure and blood biochemistry. After 3 months, the general condition of all subjects and general biochemical tests such as blood lipid, liver and kidney function, fasting blood glucose, glycated hemoglobin, insulin release test, inflammation markers and gynecological color ultrasound were tested again, and 1ml of plasma was collected and frozen in the refrigerator at -80°C.
Trial objective	
 Provide new treatments for overweight or obese patients with PCOS. Improve PCOS and establish regular menstrual cycles by reducing weight and correcting metabolic disorders.
Name and specifications of the required drugs or equipment Grid, manufacturer, and quantity	Metformin enteric coated tablets: Hebei Tiancheng Pharmaceutical Co., Ltd., trade name: Junshida, dosage: 0.5g orally 3/day; Liraglutide injection: Novo Nordisk, Denmark, trade name: Novo Nordisk, dosage: 0.6mg subcutaneous injection once a day, increased to 1.2mg after 1 week, maximum dose is 1.8 mg/d; Acetylenylestradiol cycloproterenone tablets: Bayer AG, Germany, trade name: Diane-35, dosage: 1 tablet taken orally starting from the first day of the menstrual cycle, Take 1 tablet daily for 21 consecutive days, discontinue for 7 days.

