Statistical analysis

Title of the study	The Effect of GLP-1 Agonists Versus OCs on Reproductive Disorders and Cardiovascular Risks in Overweight PCOS
NTC Number	NCT03151005
Statistical method	Statistical analyses were performed using SPSS 23.0 and GraphPad Prism 8. For normally distributed continuous variables of clinical parameters, variables are described as the mean \pm standard deviation (SD), a paired t-test was used to compare pretreatment and posttreatment values of continuous variables in each of the treatment groups, and between-group differences were compared by an independent sample t-test. For nonnormally distributed continuous variables, the nonparametric Wilcoxon signed-rank test for related samples was used to compare pretreatment and posttreatment values in each of the treatment groups. The chi-square test was used for counting data. To compare the changes in clinical parameters between different treatment groups, the nonparametric Mann-Whitney test was used. Proteomic data analysis was described by proteomic data acquisition and analysis. Protein levels are described as the mean \pm standard error of the mean (SEM), and a paired t-test was used to compare plasma protein levels measured by ELISA. Pvalues <0.05 were considered statistically significant.
Document Date	July 28, 2017

Table 1-Baseline and posttreatment characteristics of clinical parameters after 12-week of treatment.

Characteristics	CPA/EE+Met(n=30)			GLP-1 RA+Met(n=30)		
	Baseline	Posttreatment	Pvalue	Baseline	Posttreatment	Pvalue
Biometric features						
Weight(kg)						
BMI (kg/m ²)						
Waist(cm)						
WHR						
SBP(mm/Hg)						
DBP(mm/Hg)						
Reproductive function						
Dominant follicle,n(%)						
Regular menstruation, n(%)						
Amenorrhoea, n(%)*						
Oligomenorrhoea,n(%)†						
Polycystic ovaries according to Rotterdam criteria, n(%)						
T(nmol/L)						
LH(mIU/ml)						
FSH(mIU/ml)						
LH/FSH						
DHEA-S(ug/dL)						
SHBG (nmol/L)						
FAI						
E2(pg/ml)						
P(ng/ml)						
PRL(ng/ml)						
Biochemical profile of glucose metabolism						
HbA1c(%)						
HbA1c(mmol/mol)						
FBG(mmol/L)						
AUCI						
FINS(uU/ml)						
HOMA-IR						
Biochemical profile of lipid metabolism						
TG(mmol/L)						
TC(mmol/L)						

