Data are mean \pm SD or n(%). BMI, body mass index; WHR, waist-to-hip ratio; SBP, systolic blood pressure; DBP, diastolic blood pressure; T, testosterone; LH, luteinizing hormone; FSH, follicle-stimulating hormone; DHEA-S, dehydroepiandrosterone; SHBG, sex hormone-binding globulin; FAI, free androgen index; E2, estradiol; P, progesterone; PRL, prolactin. HbA1c, hemoglobin A1c; FBG, fasting blood glucose; FINS, fasting insulin; AUCI, area under curve of insulin; HOMA-IR, homoeostasis model assessment of insulin resistance; TG, triglycerides; TC, total cholesterol

Table 2-Characteristics change after treatment in this study.

Characteristics	CPA/EE +Met (n=30)	GLP-1 RA +Met (n=30)	t/z	Pvalue
Biometric features				
△Weight (kg)				
△BMI (kg/m ²)				
△Waist (cm)				
△WHR				
△SBP (mm/Hg)				
△DBP (mm/Hg)				
Sex hormones and related indicators				
△T (nmol/L)				
△LH (mIU/ml)				
AFSH (mIU/ml)				
ALH/FSH				
△DHEA-S (ug/dL)				
△SHBG (nmol/L)				
△FAI				
△E2 (pg/ml)				
△P (ng/ml)				
△PRL (ng/ml)				
Biochemical profile of lipid metabolism				
△TG (mmol/L)				
△TC (mmol/L)

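### The planned tests of change use only women with both a baseline and a 3-month value and ignore the 1-month visit; a baseline-adjusted repeated-measures model would use more of the randomised sample

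*SAP*

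**What the plan says.** The SAP's Statistical method paragraph sets out the tests. Within arms, for normally distributed variables, "a paired t-test was used to compare pretreatment and posttreatment values of continuous variables in each of the treatment groups". For the rest: "For nonnormally distributed continuous variables, the nonparametric Wilcoxon signed-rank test for related samples was used". Between arms there is an independent-sample t-test for normal variables and a chi-square test for counts. For changes: "To compare the changes in clinical parameters between different treatment groups, the nonparametric Mann-Whitney test was used". The statistic column of Table 2 is labelled t/z, so that shell can hold a t-test or a Mann-Whitney result.

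Table 1 covers two time points, as its title says: "Baseline and posttreatment characteristics of clinical parameters after 12-week of treatment". Each arm carries one n=30 over both the baseline and posttreatment columns, and Table 2 repeats it. Neither document names an analysis set or says what happens to a woman without a 3-month value.

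The Protocol's Study design row plans an examination of every participant at 1 month, covering anthropometry and then "menstrual history, hirsutism score, diet, exercise frequency and intensity, blood pressure and blood biochemistry". It plans another at 3 months: "After 3 months, the general condition of all subjects and general biochemical tests". No test or table in the SAP refers to the 1-month visit.

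**The concern.** A paired t-test, a signed-rank test and any two-sample test on changes can be computed only from complete baseline/3-month pairs. With no other rule stated, dropping incomplete pairs becomes the rule by default. Randomisation balances the women who were assigned, not those who happen to return. If those who leave one arm differ in response from those who leave the other, or leave in different proportions, the difference between arms mixes treatment effect with selection, and the error can go in either direction.

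The plan already collects data that would reduce this problem. A woman seen at 1 month and then lost has given information about her response, and the stated tests discard it. They also make no use of baseline beyond subtracting it.

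**Working it through.** **The plan's own figure.** The Protocol gives 60 under "Number of research and design cases in this center"; the shells give 30 + 30 = 60, which agrees. There is no power statement, effect size, SD or expected dropout, so nothing further can be reproduced.

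**Inputs.** From the documents: 30 per arm and a 0.05 threshold (taken as two-sided, since sidedness is not stated). Assumed: the proportion lost in each arm, *d*; the gap between completers' and dropouts' mean change, *g*, in SD units; normal data; completer SD of 1.

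**Bias of the completer comparison.** In one arm, overall mean = (1 − *d*) × completer mean + *d* × dropout mean, so completer mean − overall mean = *d* × *g*. Between arms:

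bias = *d*₁*g*₁ − *d*₂*g*₂.

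**False-positive rate with no true difference.** For the t-test, the noncentral *t* with *n*₁ + *n*₂ − 2 degrees of freedom and noncentrality bias / √(1/*n*₁ + 1/*n*₂). For Mann-Whitney, 20,000 simulated trials per row, accurate to a few tenths of a point.

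| Assumed loss | Gap | Pairs | Bias (SD) | t-test | Mann-Whitney |
|---|---|---|---|---|---|
| 20% v 20% | 0.5, 0.5 | 24/24 | 0.2×0.5 − 0.2×0.5 = 0 | 5.0% | 4.9% |
| 10% v 0% | 0.5 | 27/30 | 0.1×0.5 = 0.05 | 5.4% | 5.4% |
| 30% v 10% | 0.5, 0.5 | 21/27 | 0.15 − 0.05 = 0.10 | 6.3% | 6.0% |
| 30% v 10% | 1.0, 1.0 | 21/27 | 0.30 − 0.10 = 0.20 | 10.3% | 9.7% |
| 30% v 0% | 1.0 | 21/30 | 0.3×1.0 = 0.30 | 17.9% | 17.0% |
| 30% v 10% | 1.0, −1.0 | 21/27 | 0.30 + 0.10 = 0.40 | 27.0% | 25.3% |

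Worked row: for 0.20 SD, √(1/21 + 1/27) = 0.291, so the noncentrality is 0.20/0.291 = 0.687 on 46 degrees of freedom, giving 10.3%.

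For scale, the true difference detectable with 80% power (t-test) is 0.74 SD at 30/30 and 0.83 SD at 24/24 or 21/27.

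**What the 1-month data can recover.** Assume 30% v 10% loss, every woman seen at 1 month, and 1- and 3-month changes with unit SD and correlation *r* of 0.5 or 0.7. A woman is lost when her driving change plus independent unit-variance noise falls in the lowest 30% or 10%. The mean shift of a standard normal after cutting its lowest 30% is 0.497, and after its lowest 10% is 0.195. The driver's correlation with the selection score is 1/√2 = 0.707.

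- Loss driven by the 1-month change: completer bias at 3 months = *r* × (0.497 − 0.195) × 0.707 = *r* × 0.213, which is 0.11 SD (*r* = 0.5) or 0.15 SD (*r* = 0.7). Regressing the 3-month on the 1-month change within arm and averaging over all women brings it to about 0.
- Loss driven by the 3-month change itself: completer bias = 0.302 × 0.707 = 0.21 SD. The same model leaves 0.17 SD (*r* = 0.5) or 0.13 SD (*r* = 0.7).

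**Which rows the model can reach.** Table 2 has 18 change rows. Six are clearly measured at 1 month: weight, BMI, waist, WHR, SBP and DBP. The other 12 (ten hormone rows, two lipid rows) depend on what blood biochemistry meant at that visit. The baseline list under that term includes sex hormones but names no lipids, and the Protocol does not say whether the list carries over.

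**Counts.** If 6 of 30 women in an arm are missing and 18 of the 24 observed are regular, the observed rate is 75%, and the rate among all 30 lies between 18/30 = 60% and 24/30 = 80%.

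**The case against.** The strongest reply is that the harm is hypothetical. No loss is documented, the Protocol intends to examine every participant at 3 months, and similar loss in both arms gives no bias. The milder unequal cases raise the error rate only to 5.4% or 6.3%; 10% or more takes an assumed 1 SD gap together with clearly unequal loss. That stands, and it is why the size is given as a range starting at nil.

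A second reply is that leaving an interim visit out of a 12-week endpoint analysis is not a fault, and that a mixed model is heavy for 60 women and certain to help only 6 of 18 rows. This stands in part. Omitting the visit is not an error, but its data are already collected and offer a better analysis of those six rows at little cost.

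Two stronger readings are tempting and not supported. A reader might infer from the single n=30 that the tables presuppose no loss or would hide it. But these are blank shells, 30 + 30 matches the planned 60, and a planned number in a header is not an error. A reader might also infer that exclusion criterion f, on patients unable to finish treatment, licenses removing randomised women afterwards. It sits among the eligibility criteria, its examples are conditions knowable at entry, and the whole list is in the past tense, so screening is its most natural meaning. Neither item is a defect in itself.

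**Conclusion.** The point holds as a choice of analysis that can be improved. The stated tests are complete-pair tests that neither adjust for baseline nor use the 1-month visit, so any loss before 3 months turns the between-arm result into a completer comparison. Whether that comparison would be biased cannot be known from the documents: it requires loss that is related to response and differs between arms. Under the assumed cases the bias is 0 to 0.40 SD, against a detectable difference of 0.74 to 0.83 SD, and the false-positive rate is 5% to 27%. These are illustrations, not bounds, and the documents do not support saying that the trial's result is biased. The proposed model removes bias from loss that depends on baseline or 1-month values, and only part of it if loss depends on the unseen 3-month value; hence the sensitivity analysis. The change should be made; confidence is medium, because the structure of the tests is certain and its effect is not.

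**What to change.** 1. For weight, BMI, waist, WHR, SBP and DBP, plus any blood biochemistry items the SAP confirms were repeated at 1 month, make the between-arm analysis a baseline-adjusted arm-by-visit mixed model of all randomised women in their assigned arm, with skewed variables log-transformed. State that it assumes data are missing at random given baseline and 1-month values. Keep the t-test or Mann-Whitney on observed changes as a supporting result.
2. For the other continuous rows of Table 2, report the observed changes with the number missing in each arm.
3. Print the observed number per arm, visit and row in Tables 1 and 2. Denominators and a named analysis set alone would not supply a rule for missing values, so items 1, 2 and 4 are needed too.
4. As a sensitivity analysis, shift missing 3-month values separately by arm over a stated illustrative range, for example 0 to 1 SD in either direction, and report how each row's estimate moves. No primary outcome is named, so there is no single conclusion to overturn. At 30% v 10% loss, a 1 SD shift moves an estimate by 0.30 − 0.10 = 0.20 SD if applied to both arms alike, 0.30 or 0.10 SD if applied to one arm, and 0.30 + 0.10 = 0.40 SD if applied in opposite directions. For menstrual counts, give the range from all missing women not regular to all regular.

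The cost is about a page of SAP text, added denominators, modest extra analysis and the missing-at-random assumption. No new visits or samples are needed. Estimates may look less favourable than completer results.

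### For the ELISA proteins the SAP names only a paired t-test, so in the text supplied no comparison between the randomised arms is planned for them

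*SAP*

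**What the plan says.** The title of both documents poses a comparative question: "The Effect of GLP-1 Agonists Versus OCs on Reproductive Disorders" and cardiovascular risk. The Study design row of the protocol randomises women to a GLP-1 RA or Diane-35, with metformin in both arms. It stores plasma before treatment and again at 3 months.

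The Statistical method row of the SAP handles two kinds of data differently.

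- **Clinical parameters.** Within each arm, paired tests are used. Between arms, "between-group differences were compared by an independent sample t-test", in a sentence about normally distributed clinical parameters. For change, "To compare the changes in clinical parameters between different treatment groups, the nonparametric Mann-Whitney test was used".
- **Proteins.** "Protein levels are described as the mean" with its SEM, and "a paired t-test was used to compare plasma protein levels measured by ELISA". No other test is named for them. For the wider proteomic work the SAP says only: "Proteomic data analysis was described by proteomic data acquisition and analysis". That description is not among the documents supplied.

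SAP Table 1 (before and after, by arm) and Table 2 (change, compared between arms) list no protein. The significance rule is general: "Pvalues <0.05 were considered statistically significant".

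**The concern.** A paired t-test compares two measurements on the same woman. It cannot compare two independent groups of women, so the test named for the ELISA proteins cannot say whether the GLP-1 RA and the contraceptive affect a protein differently.

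Without a between-arm test, the available evidence on that question is the pattern of two within-arm P values. A reader who sees P below 0.05 in one arm and not in the other is likely to conclude that the effect is specific to one drug. That pattern is not a test of the difference between arms. Because both arms receive metformin, a protein change common to both is plausible here, and a within-arm test cannot separate it from the effect of the randomised drug.

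**Working it through.** **Is a between-arm test stated anywhere for proteins?** The independent-samples t-test and the Mann-Whitney test are each tied to clinical parameters by their own sentences. The Wilcoxon signed-rank sentence is worded for non-normal continuous variables in general and could cover proteins, but it is also before versus after. Table 2, the one between-arm table of change, has no protein row. So none is stated in the text supplied.

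**How misleading can two paired tests be?** The plan gives no power, effect size or SD, so there is no stated figure to reproduce.

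Inputs from the documents:
- 60 women in total (protocol) and 30 per arm (SAP table headers).
- Significance at P below 0.05 (SAP).

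Assumptions:
- All 30 women per arm are assayed; the number is not stated.
- Tests are two-sided; sidedness is not stated.
- Paired tests are run within each arm.
- The true standardised change d (mean change divided by SD of change) is the same in both arms.

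The power p of each paired t-test comes from the noncentral t distribution with n-1 degrees of freedom. The arms are independent, so P(exactly one arm significant) = p(1-p) + (1-p)p = 2p(1-p). For example, at d = 0.5, 2 × 0.754 × 0.246 = 0.371.

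| d, equal in both arms | p at n = 30 | Exactly one arm significant |
|---|---|---|
| 0 | 0.050 | 9.5% |
| 0.2 | 0.185 | 30% |
| 0.3 | 0.355 | 46% |
| 0.37 | 0.500 | 50% (maximum) |
| 0.5 | 0.754 | 37% |
| 0.6 | 0.888 | 20% |
| 0.8 | 0.988 | 2% |

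The rate is at least 30% for d from about 0.20 to 0.54, and at least 20% for d from about 0.14 to 0.60.

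A simulation of 100,000 trials at n = 30 agreed: 9.4%, 30.2%, 49.9%, 37.3% and 2.3% at d = 0, 0.2, 0.37, 0.5 and 0.8. In the same simulated trials an independent t-test on the change rejected in 4.9% to 5.1%. In a separate simulation of 4,000 trials, a baseline-adjusted between-arm test rejected in 4.8% (d = 0.3) and 4.3% (d = 0.5).

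**If fewer women are assayed,** the high rates move to larger changes:
- n = 20 per arm: 49% at d = 0.5 and 14% at d = 0.8.
- n = 10 per arm: 41% at d = 0.5, 47% at d = 0.8 and 32% at d = 1.0.

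**SEM.** With n = 30, SEM = SD/√30 = 0.18 SD, so SEM bars are √30 = 5.5 times shorter than SD bars.

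**The case against.** Several counter-arguments have force.

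- **The plan as a whole does compare the arms.** A reader might infer that the randomised comparison is never made. The documents do not support that: clinical parameters have between-arm tests and a dedicated table. The gap concerns the ELISA proteins only.
- **Within-arm testing is inferred.** The clinical sentences say that the paired tests are done in each group; the ELISA sentence does not. If the arms were pooled, the one-arm-only calculation would not apply. There would still be no between-arm test.
- **Part of the text is not supplied.** The proteomic description might contain a between-arm comparison of proteins. That cannot be ruled out, but the ELISA sentence adds none.
- **The misleading pattern depends on unstated quantities.** The SAP lays down no rule of significance in one arm only; that is an inference readers may draw. Nor can one say that the pattern will often occur: at n = 30 it is common for small to moderate shared changes and rare at d = 0.8.
- **Regression to the mean.** A reader might add this as a source of false drug effects. The eligibility criteria do not select women on protein levels, so the documents give no support for it.
- **Importance.** Proteins are absent from the stated aims (protocol Abstract and Trial objective), and no protein is named. They appear to be exploratory. This limits the weight of the point but does not remove it.
- **SEM.** Its use is a matter of presentation and does not cause the missing comparison. SD shows the spread between women, but it is not the error of a paired change either; only an interval for the change supplies that.

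**Conclusion.** The point holds for the ELISA proteins. The test stated for them cannot answer GLP-1 RA versus oral contraceptive, and nothing else in the text supplied does so. This conclusion rests on the wording alone and stands whether the paired tests are run by arm or pooled.

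The size of the harm is conditional. With by-arm testing, 30 assayed per arm and an equal true change, the chance of a result in one arm only runs from 2% to 50% over the changes examined, against about 5% for a direct between-arm test. The main clinical comparisons are untouched. Correcting how those are analysed would not repair the protein sentence, which is a rule of its own.

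**What to change.** Replace the ELISA sentence in the Statistical method row with:

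> Each ELISA protein is compared between arms by ANCOVA of the posttreatment level on arm and baseline level (log-transformed if skewed), reporting the between-arm difference or ratio with its 95% CI. Within-arm paired changes are descriptive.

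Log transformation is conditional because the documents say nothing about the distribution of the proteins. An independent t-test on the change would also hold the 5% level if a simpler method is preferred.

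State how many women per arm are assayed and what is paired. As a secondary change, show SD for spread and the 95% CI of the paired change in place of SEM.

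The cost is SAP wording and one model per protein. Plasma is already stored at both visits, so no new sampling is needed if the ELISA uses those samples. Some within-arm significant results would lose their headline. Power is limited: with 30 per arm, a between-arm t-test on change has 80% power for a difference of about (1.960 + 0.842) × √(2/30) = 0.72 SD of change (normal approximation), so the interval should carry the interpretation.

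### The supplied documents name no primary endpoint and no multiplicity rule, so 18 between-arm comparisons at P<0.05 leave the headline result open to choice after the data are seen

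*SAP*

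**What the plan says.** The SAP's Statistical method section closes with its only criterion for a positive finding: "Pvalues <0.05 were considered statistically significant". It applies to every test in the plan.

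Two sentences cover continuous comparisons between arms. For normally distributed variables, "between-group differences were compared by an independent sample t-test". For changes from baseline, "To compare the changes in clinical parameters between different treatment groups, the nonparametric Mann-Whitney test was used". A third sentence covers count outcomes without saying whether the comparison is within or between arms: "The chi-square test was used for counting data".

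The between-arm results go into the shell headed "Table 2-Characteristics change after treatment in this study", which has one test-statistic column and one P value column. Table 1 gives P values within each arm only. It includes the row "Regular menstruation, n" (%), which has no counterpart in Table 2 as supplied.

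The protocol's aims are broad. The Abstract sets out to observe effects on glucose, lipids, sex hormones and the menstrual cycle. The Trial objective entry adds: "Improve PCOS and establish regular menstrual cycles by reducing weight and correcting metabolic disorders". Neither document labels an outcome primary, orders the outcomes, calls an analysis exploratory or describes an adjustment for multiple testing of the clinical parameters.

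**The concern.** A 5% threshold limits the error of one test. It does not limit the error of the conclusion that one regimen differs from the other when that conclusion may rest on any of many tests. The stated aims cover four domains and no outcome is singled out, so whichever row falls below 0.05 can be presented as the main finding after the results are known. A reader of the eventual report could not tell a result that was sought in advance from one picked out of 18.

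**Working it through.** The plan states no family-wise error rate, power or sample-size derivation, so there is no figure of its own to reproduce.

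**Inputs**
- Threshold: 0.05 per test (SAP, Statistical method). Sidedness is not stated; two-sided is assumed.
- Between-arm rows in SAP Table 2 as supplied: 6 biometric + 10 sex-hormone and related + 2 lipid = 18. Table 1's within-arm P values are left out because they do not compare the regimens.
- Arm size: 30 (column heads of Tables 1 and 2).
- Correlation between rows: not given anywhere. Every value below is an assumption.

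**Step 1. Expected false positives if no row truly differs.** 18 × 0.05 = 0.9. This holds for any correlation.

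**Step 2. Chance of at least one, independent rows.** 1 − 0.95^18 = 0.603. For jointly normal statistics tested two-sided, this is the upper limit.

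**Step 3. One common correlation r.** With c = 1.96, the chance is 1 − ∫ φ(u) [Φ((c − √r·u)/√(1−r)) − Φ((−c − √r·u)/√(1−r))]^18 du.

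**Step 4. Correlation within the three Table 2 families only.** Let Q(k, r) be the integral in Step 3 with exponent k. The chance is 1 − Q(6, r)·Q(10, r)·Q(2, r).

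| Assumed r | Common to all 18 rows | Within families only |
|---|---|---|
| 0.3 | 0.509 | 0.555 |
| 0.5 | 0.398 | 0.486 |
| 0.7 | 0.277 | 0.397 |
| 0.9 | 0.151 | 0.277 |

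**Step 5. Does the choice of test matter?** In 20,000 simulated trials per setting, with 30 per arm and 18 equally correlated normal rows at r = 0, 0.5 and 0.9, the t-test gave 60.8%, 40.3% and 15.2%. The Mann-Whitney test gave 60.3%, 41.0% and 15.9%. Which of the SAP's two between-arm tests is used barely changes the result.

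**Step 6. Only some rows null.** With 10 truly null rows (assumption), 10 × 0.05 = 0.5 false positives are expected. The chance of at least one is 0.401, 0.287 and 0.128 at common correlations of 0, 0.5 and 0.9.

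**Step 7. Sidedness.** One-sided testing at 0.05 leaves the independence figure at 60% and gives about 32% and 13% at common correlations of 0.5 and 0.9.

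**The case against.** The strongest reply has four parts.

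**Size.** A reader might take 60% as this trial's error rate. The documents do not support that. The figure needs independent rows and no true difference on any row. Weight overlaps BMI, and the LH/FSH ratio is built from two other rows, so exact independence is ruled out. The protocol's Abstract also makes some real differences plausible: "As a classic PCOS drug, CPA/EE is mainly used to adjust estrogen and progesterone levels and menstrual cycle". This part stands. 60% is a ceiling, and the expected count and the range across assumptions are the better summary.

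**Reproductive outcomes.** A reader might also infer that regular cycles are the only reproductive goal and are never compared between arms. That goes too far. The Abstract names sex hormones as well, and most of Table 2's ten hormone rows report them. The chi-square test could be applied between arms to menstrual regularity. All that can be said is that regularity has no between-arm row in Table 2 as supplied.

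**Count.** Table 2 as read has no glucose rows, although Table 1 has six, so rows may have been lost in extraction. Count outcomes may also be compared between arms. Either would raise the number of tests, so 18 errs on the low side.

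**Intent.** The protocol's language is partly descriptive, and nothing in the SAP says that one significant row establishes a difference between regimens. This softens the point but does not remove it. The trial is randomised, a significance rule is stated, and no analysis is labelled exploratory. Whether an outcome is ranked outside these two documents cannot be checked here.

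**Conclusion.** The gap is real and should be closed; confidence is high. Within the supplied documents, every between-arm row is tested at 0.05 with nothing ranked and nothing adjusted.

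Under no true difference on any row, the expected number of false positives is 0.9. The chance of at least one is 28% to 56% in the within-family model and 15% to 40% at common correlations of 0.9 to 0.5, with 60% as the upper limit. Even the lowest of these, 15%, is three times the nominal 5%. If only 10 rows are null, the expected number is 0.5 and the chance 13% to 40%.

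These figures rest on assumed correlations, two-sided testing and the row count as supplied. They describe the risk of some false positive row. They do not show that any particular claim will be false.

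**What to change.** Before outcome data are seen, the sponsor should:

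1. Name one between-arm primary endpoint drawn from its stated aims, define it, and test it at two-sided 0.05.
2. Adjust the remaining between-arm clinical rows by Holm or Benjamini-Hochberg, or label them exploratory with no confirmatory claim.

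If outcome data have already been seen, all rows should be labelled exploratory.

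The sponsor keeps the choice of endpoint. If menstrual regularity is considered, two matters come first. The sponsor must confirm that it is recorded at 3 months: the protocol's Study design lists menstrual history at 1 month but not by name at 3 months, whereas SAP Table 1 implies a 12-week value. It must also address that the comparator is itself given cyclically, so regularity scored on treatment may partly reflect dosing. A yes/no outcome is coarse as well. With 30 per arm, the chi-square test has 80% power only for a difference of about 30 to 35 percentage points (32 to 38 with continuity correction), if the lower arm's rate is 20% to 60% (assumption).

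**Cost.** The change is SAP wording, plus a between-arm row if the chosen endpoint has none in Table 2. The real price is fewer significant secondary rows. For a two-sample t-test with 30 per arm, the difference detectable with 80% power is 0.736 SD at 0.05. At Holm's strictest step it is 1.024 SD if 17 rows remain (0.05/17), or 1.030 SD if the primary lies outside Table 2 and all 18 remain (0.05/18). Power for a 0.736 SD difference falls from 80% to 41% or 40%. The exploratory label avoids this loss but gives up confirmatory claims on those rows.
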